Overview of the Trial: This study is a randomized trial of the video in 50 AYAs with advanced cancer and their caregivers that will assess preferences for care in advanced cancer and concordance rate of preferences between dyad. We will randomly assign dyads to one of two ACP modalities: 1. the ACP video decision aid (intervention), or 2. Usual care. Patients' and caregivers' knowledge, preferences (goals of care, CPR, ventilation), and decisional conflict be assessed before and after exposure to the video or control ACP modality. Telephone-based interviews will be conducted at 3 months to assess patients' and caregivers' preferences, ACP conversations with caregivers and clinicians, and the medical record will be queried to examine ACP documentation. The primary outcome is AYA and caregiver concordance regarding treatment preferences for advanced cancer (Aim 1). Secondary outcomes include knowledge, preferences, decisional conflict, and ACP engagement (Aims 1 and 2). We will also explore the stability of preferences, presence of ACP conversations and documentation after 3 months (Aim 2). We hypothesize that the video decision aid better informs patients and their caregivers and leads to more informed decision making.

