6.0 Study Timelines

Participants enrollment in the study will last the course of 3 months with one inperson study visit and one phone-based interview. The study entails a one-time 30-40 minute in-person visit or over Zoom where participants will be randomized to the video aid intervention or information sheet control. Around three months following this initial visit, participants will complete a 5-10 minute follow-up phone-based interview. This follow-up interview will be audio recorded with the participants' knowledge and transcribed for analysis. Participants will have consented to be audio recorded during the informed consent process. All recordings will be de-identified. Given the number of AYA patients typically treated at this institution, we anticipate the study to span 2 years, including 3month data collection tools preparation and survey training, 16 months rolling recruitment, surveying, and 3-month follow-up, 2 months data cleaning, analysis, and manuscript preparation. This timeline will continue to be updated given changes to recruitment/enrollment strategies in the setting of COVID-19.

7.0 **Procedures Involved**

Study design, randomization, intervention, and control arm: We will conduct a randomized controlled trial in 50 AYA with advanced cancer and their caregivers who

will be randomized as dyads to either the video (intervention) or usual care (control) (Figure 1). After enrollment, we will collect the following information from the caregiver: full name, date of birth, zip code, and gender for the purposes of reporting to the NCI and subject level registration.

Figure 1. Data collection time periods for the proposed study.

The interview script for the encounter with participants is provided in Appendix C. Following completion of the pre-intervention questionnaire (Appendix D), the RA will provide a brief explanation of the three types of care (life-prolonging, selective, comfort) and the subjects will be randomized to intervention or usual care. Patients and caregivers in the control group will only receive the verbal description of the three types of care (Appendix C, page 1).

Randomization: We will use a central, computer-generated simple randomization design stratified by race and ethnicity for even recruitment in both arms of the study.

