Data elements of survey questionnaire: We are interested in studying the influence of the video compared to enhanced usual care on medical care options and concordance rate with 50 AYA with advanced cancer and their caregivers. To assess study outcomes, data will be collected, to the extent possible, using validated tools. Table 1 outlines the data elements that will be obtained from both patients and caregivers. The audio recording and de-identified transcripts will be stored in a stored location on a secured network only accessible to the study team. The audio recording and de-identified transcripts will be stored in a stored location on a secured network only accessible to the study team.

Sociodemographics: Data on sociodemographics will include age, gender, race, ethnicity, health insurance, education, marital status, religion, and religious attendance. (Appendix D, page 1-2, questions 1-8).

Preferences: Patients and caregivers will be asked for their goals-of-care preference (lifeprolonging, selective, comfort, or Unsure), CPR preference (Yes, No, or Unsure), and ventilatory support (Yes, No, or Unsure) at baseline, and then again immediately after watching the video or reviewing the informational sheet (Appendix D, page 4, question 1-3; Appendix H, page 1, question 1-3) and then we will contact all patients after 3 months by telephone to ask for their preferences.(11, 13, 20) (Appendix I, page 2-3, question 1-3). We will also have an open-ended question for those patients who change their preferences from the initial post-video or control survey ("Can you explain why you have changed your preference from the one stated three months ago?"). AYAs and caregiver concordance of preferences (i.e., the same preference) is our primary outcome.

Knowledge: We will ask five true/false questions and one multiple choice question regarding knowledge of goals-of-care options which were used and validated in our previous studies.(11, 13, 20) (Appendix D, page 6; Appendix H, page 3).

Decisional conflict: We will measure decisional conflict, which attempts to measure uncertainty regarding decision making.(52) The Decision Conflict Scale is a wellvalidated and commonly used tool, we will use the 4-item SURE scale for ease of use and to reduce burden on the participant.(52) (Appendix D, bottom of page 4, questions 1-4; Appendix H, bottom of page 1, questions 1-4).

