ACP engagement: We will ask four validated questions to patients only regarding ACP engagement (How ready are you to talk to your caregiver? To your doctor? To appoint a surrogate? To sign an ACP document?).(54) (Appendix D, page 4; Appendix H, page 2).

Comfort with the video: For those patients and caregivers randomized to the video, we will measure acceptability of the decision aid using four questions regarding comfort viewing the video, which we have validated in our prior work.(11, 13, 15, 17, 20-22, 25, 46) (Appendix H, page 4).

Additional outcomes: AYA-reported ACP conversations with caregivers and clinicians will be assessed after three months from baseline survey. Both patients and caregivers will be asked about ACP conversations (Appendix I, bottom of page 3).

Data collection protocol: Based on our prior work, data collection is estimated to take no longer than 40 minutes (10 minutes for informed consent and screening; 10 minutes for baseline assessment; 10 minutes for ACP modality; 10 minutes for immediate follow-up interview) and will be conducted in the outpatient setting. The relatively brief interviewing time (40 minutes) in which the survey is conducted should assure completion of the interview without burdening participants. We do not foresee the additional time to complete the survey to be a barrier to successful recruitment and completion of the protocol.

Participants will be provided written copies of the questions or the questions will be shared with them over zoom (using the "share screen" feature) in order to follow along

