Aim 1: H1: AYA with advanced cancer and caregivers randomized to the video will have higher concordance between patients and caregivers (Primary Outcome), and more likely to have higher knowledge, make decisions for less burdensome care (i.e., limited or comfort care, no CPR, no ventilatory support), have lower decisional conflict, and engagement, than those randomized to the control group. Preference concordance between patient and caregiver will be treated as a dichotomized variable and compared between the two study arms using a chi-square test. We will conduct separate analyses for patients and caregivers for secondary outcomes. Knowledge score, decision conflict scale, and ACP engagement will be considered as continuous variables. We will use twosample t-tests or Wilcoxon rank sum tests, whichever more appropriate, to compare the distribution between the two study arms. Chi-square tests will be used to compare the proportion of patients/caregivers choosing less burdensome care between the two study arms. We will explore the effect of patient characteristics (age, sex, etc.) in choosing less invasive care using a logistic regression model. In this study, we will treat sex as selfreported gender and will conduct a sex-based analysis of intervention effects to explore sex as a biological variable. *Power analysis*: Assuming 50% of control arm achieve preference concordance between patients and caregivers, the study will have 80% power to detect a 41% difference (50% vs. 89%) in concordance. Assuming 68% of control patients/caregivers choose non-life prolonging care, the study will have 82% power to detect a 31% difference (68% vs. 99%) in preferences between the two arms. For the continuous outcomes (knowledge, decisional conflict, ACP engagement), the study will have 80% power to detect an effect size of 0.81 with 25 subjects per group.

Aim 2: *H2.* Patients randomized to the video will have more ACP conversations and documentation after 3 months. We will treat conversations and documentation as continuous variables. Assuming 50% of controls achieve ACP conversations/documentation between baseline and three-month follow-up, the study will have 81% power to detect a 27% difference (50% vs. 77%) between the two study arms.

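### The Aim 1 knowledge comparison gives no role to the baseline score the trial collects, and Table 1 and the text disagree on whether decisional conflict and ACP engagement have baselines

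*Combined protocol and SAP*

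**What the plan says.** **Analysis.** Section 8.0, Data Analyses, Aim 1 says of the three scores: "Knowledge score, decision conflict scale, and ACP engagement will be considered as continuous variables". It continues: "We will use twosample t-tests or Wilcoxon rank sum tests, whichever more appropriate, to compare the distribution between the two study arms". It names no baseline covariate and does not say whether the post-exposure score or a change score is compared. Patients and caregivers are analysed separately for secondary outcomes. The power statement gives 80% power for an effect size of 0.81 with 25 per group.

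**Knowledge.** The instrument is "five true/false questions and one multiple choice question regarding knowledge of goals-of-care options", located at "Appendix D, page 6; Appendix H, page 3". Section 7.0 identifies the first of these appendices as the questionnaire given before the intervention: "Following completion of the pre-intervention questionnaire (Appendix D". Table 1 lists knowledge both at baseline and after exposure.

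**Decisional conflict and engagement.** The trial overview in Section 2.0 has "decisional conflict be assessed before and after exposure to the video or control ACP modality". Section 8.0 places the decisional conflict items at "Appendix D, bottom of page 4, questions 1-4; Appendix H, bottom of page 1, questions 1-4" and the engagement items, asked of patients only, at "Appendix D, page 4; Appendix H, page 2". Table 1 lists both measures only after exposure.

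**Randomisation.** Section 7.0 describes a central, computer-generated design that it calls simple, with race and ethnicity as strata, and gives even arms as the reason. It names no blocks, minimisation or other balancing device.

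**The concern.** The trial is small, and by its own figures can detect only a large effect on the scores. A baseline measured on the same instrument is the obvious way to gain precision. For knowledge it is already collected, yet the analysis gives it no part.

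The disagreement over the other two measures has a practical side. A baseline not taken before exposure cannot be recovered later, so staff need to know whether to collect it and the analyst needs to know whether it will exist.

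On randomisation, independent draws within strata have the same distribution of arm totals as independent draws without strata. As written, the stratification does not serve its stated purpose.

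**Working it through.** **Inputs.** From Section 8.0, Aim 1: 25 per arm, effect size d = 0.81, 80% power. Assumed: two-sided alpha of 0.05 (none is stated), and a baseline-to-post correlation r from 0 to 0.7 (none is given).

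**1. The plan's own figure.** For a two-sample t-test the noncentrality is d / √(1/25 + 1/25) = 0.81 / 0.2828 = 2.864, with 48 degrees of freedom and critical value 2.011. Power is 80.1%, and the effect detectable with 80% power is 0.809. A one-sided 0.05 test would give 88.1%, which does not match. The stated figure is therefore that of an unadjusted comparison.

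**2. ANCOVA on baseline.** The residual variance is multiplied by (1 − r²), and by 1 + 1/46 for chance imbalance in the covariate. The error degrees of freedom are 47. The noncentrality becomes 2.864 / √[(1 − r²)(1 + 1/46)]. At r = 0.5 this is 2.864 / √(0.75 × 1.0217) = 3.271.

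| r | Detectable effect | Power at 0.81 |
|---|---|---|
| t-test | 0.81 | 80% |
| 0 | 0.82 | 79% |
| 0.2 | 0.80 | 81% |
| 0.3 | 0.78 | 83% |
| 0.5 | 0.71 | 89% |
| 0.7 | 0.58 | 97% |

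**3. Coarse scores.** Six items give a 0–6 score if each counts one point (assumed). Simulation with 20,000 trials per scenario, cutting latent normal variables into seven levels, gave:

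| Score | t-test | ANCOVA at r = 0, 0.2, 0.3, 0.5, 0.7 |
|---|---|---|
| 0–6, symmetric | 78% | 77, 79, 81, 86, 95% |
| 0–6, 21% of controls at the top (assumed) | 74% | 73, 74, 76, 82, 92% |

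The type I error of ANCOVA was 4.6 to 5.2% throughout.

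**4. If the video weakens the baseline link.** With r = 0.5 in controls and 0 in the video arm, ANCOVA against the t-test gives 82.3% against 80.4% (continuous), 79.3% against 77.8% (0–6) and 75.2% against 73.9% (0–6 with ceiling). The gain is 1 to 2 points.

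**5. Change score.** Its standard deviation is √[2(1 − r)] times that of the post score, so the detectable effect is 0.809 × √[2(1 − r)]. That is 0.957 at r = 0.3, 0.809 at r = 0.5 and 0.626 at r = 0.7. It beats the post score only when r exceeds 0.5, and ANCOVA is better at each of these values.

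**6. Which baselines the documents support.**

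| Measure | Overview (2.0) | Instrument text (8.0), with Appendix D as pre-intervention (7.0) | Table 1, baseline |
|---|---|---|---|
| Knowledge | yes | yes | yes |
| Decisional conflict | yes | yes | not listed |
| ACP engagement | not mentioned | yes | not listed |

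**7. Randomisation.** With simple draws the number in one arm is Binomial(50, 0.5). P(25/25) = 11.2% and P(30/20 or worse) = 20.3%. In a stratum of 10 dyads (size assumed), P(7/3 or worse) = 34%. A 30/20 split lowers t-test power from 80.1% to 78.5%. For the primary comparison at 50% against 89%, chi-square power falls from 89.1% to 86.0–87.4% without continuity correction, and from 80.1% to 79.1% with the Yates correction. The cost is 1 to 3 points.

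**The case against.** The strongest reply is that nothing here is an error. The unadjusted tests are approximately valid, the power figure reproduces, and the scores are secondary outcomes in a pilot. The gain rests on a correlation the documents do not give. At r = 0.3 or below it is 3 points or less, and a teaching video could well weaken the baseline link. All of that stands. It limits the size of the point but does not remove it, because the baseline is already collected and the modelled downside is about 1 point.

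Three stronger readings are tempting and should be resisted.

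- A reader might infer that the plan compares post-exposure scores only. It does not say so, and a change score is not excluded. What can be said is that no role for baseline is specified.
- A reader might infer from Table 1 that decisional conflict and engagement have no baseline, or that the matter is wholly open. The text leans towards collection. Table 1 is also visibly incomplete: its baseline part omits the sociodemographic items and its 3-month part omits ACP documentation. Omission there is weak evidence. The conflict is real, but probably a table to correct.
- A reader might infer that simple randomisation cannot give even arms, or that permuted blocks are required. An even split can arise by chance; the method just does not ensure it. The word simple may also be loose wording for a balanced list. Blocks carry a cost: the research assistant who randomises is unblinded, and someone always guessing the arm that is behind in the stratum would be right about 67% of the time with blocks of 4, 6 and 8, against 50% with simple draws.

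**Conclusion.** The point holds as a matter of precision and clarity in secondary outcomes. The knowledge analysis gives no role to a baseline that the overview, the instrument text and Table 1 all place before exposure. Adjustment changes power at an effect of 0.81 from 80% to between 79% and 97% for r from 0 to 0.7. It adds only 1 to 2 points if the video weakens the baseline link. These figures assume two-sided 0.05, 25 analysed per arm and the correlations shown.

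The disagreement between Table 1 and the text on decisional conflict and engagement needs resolving, though the text favours a baseline for both. The randomisation wording is a lesser matter, because the stated method does not ensure the stated balance and imbalance costs only 1 to 3 power points. None of this threatens the primary concordance result.

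**What to change.** 1. Make ANCOVA on the baseline score the analysis of knowledge, separately for patients and caregivers, with the planned t-test or Wilcoxon test as a sensitivity analysis. This also settles whether a post or a change score is meant. It costs a sentence of SAP text and no new data, with about 1 power point at risk if baseline is uninformative.
2. Reconcile Table 1 with the overview in Section 2.0, the procedures in Section 7.0 and the instrument paragraphs in Section 8.0. If decisional conflict and engagement are collected at baseline, analyse them by the same ANCOVA (engagement in patients only). This costs a corrected table.
3. In Section 7.0, state the balancing method actually used or drop the claim of evenness. Permuted blocks for dyads not yet randomised are optional. They would need a new allocation list, and their greater predictability to an unblinded research assistant has to be weighed against a small power cost. The documents do not say how many dyads remain.

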during the face-to-face or virtual interviews. The RA will collect baseline data, randomize patients and caregivers as a dyad to either the video or control arm via concealed envelopes, and administer the intervention. After this baseline interview and randomization, the RA will collect the remaining outcomes data regarding preferences, knowledge, and decisional uncertainty from both the patient and caregiver. For those participants randomized to the video intervention, they will also be asked questions regarding the usefulness of the video and their comfort with the video. If patients express interest in creating their own video, RA's may provide an information sheet to guide them through the process (Appendix J). Both patients and caregivers will be contacted at 3 months and assess their preferences and ACP conversations at that time. These phonebased interviews will be conducted independently to reduce influence on the outcome of concordance and will be audio recorded for later analysis.

Table 1: Data Element and Sources									
		SOURCE							
Data Collected	Purpose	Tool	By Whom	From	When	Note			
1. Eligibility screen									
Advanced Cancer	target sub-population identification, covariate		RA, PO	EHR	Daily	HIPAA waiver			
Cognitive Assessment	screening	SPMSQ	RA	interview	Outpatient/Vir tual				
2. Baseline Assessment									
Preferences	2º outcome		RA	interview	Outpatient/Vir tual				
Knowledge	2º outcome		RA	interview	Outpatient/ Virtual				
Randomization followed by video intervention or enhanced usual care									
3. Post-video or informational sheet									
Preferences	2º outcome		RA	interview	Outpatient/ Virtual				
Preference concordance	1º outcome		RA	interview	Outpatient/ Virtual				
Knowledge	2º outcome		RA	interview	Outpatient/ Virtual				
Decisional conflict	2º outcome	DCS	RA	interview	Outpatient/ Virtual				
ACP engagement	2º outcome	ACPE	RA	interview	Outpatient/ Virtual	AYA only			
Comfort with video	2º outcome		RA	interview	Outpatient/ Virtual	Video arm			
4. Follow-up at 3 months									
Preferences	2º outcome		RA	telephone					
ACP conversations	2º outcome		RA	telephone					

KEY: RA: Research Assistant; PO: Primary Oncologist; EHR: Electronic Health Record; SPMSQ: Short Portable Mental Status Questionnaire; DCS: Decisional Conflict Scale; ACPE: Advance Care Planning Engagement Questionnaire.

DATA ANALYSES

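### The treatment-preference tests leave out each participant's own pre-randomisation answer, which costs conditional validity and some precision but does not bias the comparison

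*Combined protocol and SAP*

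**What the plan says.** Section 8.0 (Preferences) has patients and caregivers state a goals-of-care, a CPR and a ventilation preference "at baseline, and then again immediately after watching the video or reviewing the informational sheet", with a further contact at 3 months. The first answer comes before allocation. Section 7.0 states: "Following completion of the pre-intervention questionnaire (Appendix D), the RA will provide a brief explanation of the three types of care", with randomisation after that. The data collection paragraph of section 8.0 gives the same order: "The RA will collect baseline data, randomize patients and caregivers as a dyad to either the video or control arm via concealed envelopes".

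Under DATA ANALYSES, Aim 1, the comparison of these preferences is: "Chi-square tests will be used to compare the proportion of patients/caregivers choosing less burdensome care between the two study arms". Secondary outcomes are analysed separately in patients and in caregivers, so each test has 25 per arm. No time point is named for this test. Table 1 lists preferences as a secondary outcome at baseline, just after exposure and at 3 months; the immediate post-exposure answer is the likely reading.

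The only regression planned for preferences is an exploratory logistic model of patient characteristics such as age and sex, which names neither arm nor baseline preference. The mixed-effects models under Missing Data are there to handle incomplete data. On allocation, section 7.0 says: "We will use a central, computer-generated simple randomization design stratified by race and ethnicity". Baseline preference is therefore not balanced by design.

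The stated power is: "the study will have 82% power to detect a 31% difference (68% vs. 99%) in preferences between the two arms".

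**The concern.** The baseline answer to the same item, given earlier in the same visit, is probably the best available predictor of the post-exposure answer, and the video cannot have affected it. With 25 per arm and no stratification on preference, the arms may differ on that item before anyone sees the video. If they do, part of the post-exposure difference was already there, and an unadjusted test cannot separate it from an effect of the video.

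There are six such comparisons (three items, two populations). The trial is a pilot meant to support a larger one, so the hypothesis about preferences (H1b) could be credited or dismissed partly on a chance imbalance. If adjustment is added only after an imbalance has been seen, it will look post hoc.

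**Working it through.** **Inputs from the documents.** 25 per arm; 68% control vs 99% video choosing non-life-prolonging care; stated power 82%; patients and caregivers tested separately.

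**Assumptions.**
- Two-sided 0.05, because the documents state no alpha.
- Baseline rate 68% in both arms. The documents give 68% only as a control-arm outcome rate, for goals of care; they give no baseline rate and no rate for CPR or ventilation.
- Control-arm correlation between baseline and post-exposure answers of 0.3 to 0.7, with zero also shown. The documents give none.

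**Step 1: the plan's figure.** Exact enumeration over two binomials (n = 25, 0.68 and 0.99) gives 82.3% for Fisher's exact test, which matches the stated 82%. The same enumeration gives 94.5% for the uncorrected Pearson chi-square and 79.1% with the Yates correction. The text says chi-square without mentioning a correction.

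**Step 2: size of chance imbalance.** The standard deviation of the between-arm baseline difference is sqrt(2 × 0.68 × 0.32 / 25) = sqrt(0.0174) = 0.132, or 13.2 points. For two independent Binomial(25, 0.68) counts, the probability of a difference of 4 or more people (4/25 = 16 points) is 0.288, and of 5 or more (20 points) 0.171.

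**Step 3: how much carries through.** With no true effect and equal rates at both times, the expected shift in the outcome difference is roughly the correlation times the baseline gap. For a 16-point gap this is 0.3 × 16 = 4.8 to 0.7 × 16 = 11.2 points.

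**Step 4: false-positive rate.** Simulation with no true effect, 40,000 trials:

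| Control-arm correlation | Chi-square, given a baseline gap of 4 or more | Mantel-Haenszel stratified by baseline, same trials |
|---|---|---|
| 0.3 | about 7% | 4-5% |
| 0.5 | about 10% | 4-5% |
| 0.7 | about 14% | 4-5% |

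Over all randomisations the chi-square rate is about 5%.

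**Step 5: power, uncorrected chi-square against uncorrected Mantel-Haenszel stratified by baseline answer.**

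| True rates | Chi-square | Change from stratifying, correlation 0.3 to 0.7 |
|---|---|---|
| 68% vs 99% | about 94% | -1 to +3 points |
| 68% vs 95% | about 76% | 0 to +11 points |
| 68% vs 90% | about 51% | 0 to +16 points |

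At zero correlation, stratifying costs about 1 to 3 points.

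**Step 6: power, Fisher's exact test against the exact test stratified by baseline answer.**

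| True rates | Fisher | Stratified, correlation 0 | Stratified, 0.32 | Stratified, 0.70 |
|---|---|---|---|---|
| 68% vs 99% | 82% | 86% | 89% | 95% |
| 68% vs 95% | about 62% | about 64% | 69% | 80% |
| 68% vs 90% | about 36% | 40% | 43% | 57% |

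The zero-correlation column is the part of the gain that comes from the stratified test being less discrete. At 68% vs 99% that is 86 - 82 = 4 points, with no help from the baseline answer.

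**The case against.** The strongest reply is that the planned test is valid. Randomisation makes the unadjusted comparison unbiased, and chance imbalance is already counted in its 5% error rate. That stands. A reader might infer from the missing baseline term that the preference results will be biased; the documents do not support that. What remains is a false-positive rate conditional on the allocation obtained, and some lost precision.

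A second reply is that almost no power is lost at the plan's own effect. For the uncorrected chi-square this is right, since power is already about 94%. A reader might infer a large loss from Fisher's exact test or from continuity-corrected or permutation tests, where the apparent gain is bigger. Part of the exact and permutation gain is reduced discreteness, and the analysis text names none of these tests. In fairness, the stated 82% does reproduce with Fisher's test, so which test the plan intends is not settled.

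Third, it is tempting to say that about two thirds of participants have already chosen less burdensome care before exposure, or to set the 13-point standard deviation directly against the 31-point target. Neither is supported. The 68% is an outcome rate, and the baseline question comes before the explanation of the three types of care. Only part of a baseline gap carries through. In a 99% video arm with a 68% baseline, the correlation cannot exceed (0.68 - 0.68 × 0.99) / sqrt(0.68 × 0.32 × 0.99 × 0.01) = 0.0068 / 0.0464 = 0.15, so the 0.3 to 0.7 range describes the control arm only.

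Finally, these are secondary outcomes in a pilot. That limits the weight of the point, but the correction is nearly free.

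**Conclusion.** The point holds as a matter of conditional validity and precision. The plan collects a pre-randomisation answer to each preference item and does not use it in the test of that item. If the baseline rate is 68%, roughly 29% of trials would have a baseline gap of 4 or more people. In those trials the chi-square false-positive rate would be about 7% to 14% for correlations of 0.3 to 0.7, where the stratified test stays at 4% to 5%.

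The power case is modest: negligible at the planned 68% vs 99%, and up to 11 or 16 points if the video arm reaches only 95% or 90%. All of this rests on an assumed baseline rate, correlation and alpha, and on reading the test as the immediate post-exposure comparison. A substantial correlation is plausible because the items are repeated within one 30-40 minute visit, but it is not documented.

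**What to change.** In DATA ANALYSES, Aim 1:

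- State that the preference comparison uses the immediate post-exposure answer, if that is what is meant.
- For each of the three items, separately in patients and in caregivers, make the main test a Mantel-Haenszel or exact test stratified by the participant's own baseline answer to that item.
- Prespecify how Unsure is grouped, both in the baseline strata and in the outcome.
- Report a stratified risk difference with a small-sample confidence interval. Avoid ordinary logistic regression as the main analysis, because a 99% video-arm rate leaves nearly empty cells.
- Keep the unadjusted chi-square as a supporting analysis, and report the baseline-by-post table for each arm.

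The cost is analysis-plan wording and a few lines of code, with no new data or participants. There are two downsides. One stratum will be sparse, about 25 × 0.32 = 8 per arm if the baseline rate is 68%. Power falls by about 1 to 3 points (Mantel-Haenszel against the uncorrected chi-square) if the baseline answer turns out not to predict the later one.
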